6.2 Radiation Therapy Adverse Events

All patients will be seen in the radiation oncology department during radiation therapy. Any observations regarding radiation reactions will be recorded and should include attention to the following potential side effects:

- Small bowel or rectal irritation manifesting as abdominal cramping, diarrhea, rectal urgency, proctitis, or hematochezia
- Bladder complications including urinary frequency/urgency, dysuria, hematuria, urinary tract infection, and incontinence
- Radiation dermatitis

Clinical discretion may be exercised to treat side effects from radiation therapy. Examples of typical medications used in the management of side effects, such as diarrhea, include diphenoxylate or loperamide. Bladder or rectal spasms are usually treated with anticholinergic agents or tolterodine. Bladder irritation may be managed with phenazopyridine. Erectile dysfunction is often treated with medical management or mechanical devices. A record of the incidence and management of side effects will be recorded in the electronic medical record as a usual course of care and the data will be reported in a Case Report Form.

Definition of an Adverse Event (AE): Any unfavorable and unintended sign (including an abnormal laboratory finding), symptom, or disease temporally associated with the use of a medical treatment or procedure regardless of whether it is considered related to the medical treatment or procedure (attribution of unrelated, unlikely, possible, probable, or definite). [CTEP, NCI Guidelines Adverse Event Reporting Requirements. January 2005; <http://ctep.cancer.gov/reporting/adeers.html>]

Definition of an SAE: Any adverse experience occurring during any part of protocol treatment and 30 days after that results in any of the following outcomes:

- Death
- A life-threatening adverse experience
- Inpatient hospitalization or prolongation of existing hospitalization
- A persistent or significant disability/incapacity
- A congenital anomaly/birth defect

Important medical events that do not result in death, are not life threatening, or do not require hospitalization may be considered an SAE, when, based upon medical judgment, they may jeopardize the patient and may require medical or surgical intervention to prevent one of the outcomes listed in the definition.

This study will utilize the NCI Common Terminology Criteria for Adverse Events (CTCAE) version 4 for reporting of adverse events (AEs). The CTCAE version 4 is identified and located on the CTEP web site at: http://ctep.cancer.gov/protocolDevelopment/electronic_applications/ctc.htm. All appropriate treatment areas should have access to a copy of the CTCAE version 4.

The SAEs will be reported per Case Comprehensive Cancer Center policy.

Significance of Adverse Event	Study Related (Possible/Probable/Definite)		Not Study Related (Unrelated/Unlikely)	
Attribution of Adverse Event	Expected	Unexpected	Expected	Unexpected
Fatal Events (Grade 5)	5 working days	5 working days*	Summarize in Continuing Review	10 working days
Life-Threatening or disabling (Grade 4)	Summarize in Continuing Review	10 working days	Summarize in Continuing Review	Summarize in continuing review report
Severe and undesirable (Grade 3)	Summarize in Continuing Review	10 working days	Not reportable to IRB	Summarize in continuing review report
Moderate and Mild Grades 1 & 2	Not reportable to IRB			
Unanticipated Problem that is a reportable Event	5 working days and reportable to HHS agency head and OHRP			

*All study related, unexpected deaths should be carefully assessed against the definition of unanticipated problem.

The SAE is to be entered into Oncore and the regulatory coordinator and DSTC coordinators will then work with the PI to submit it to the IRB and DSTC. The SAE is to be placed into Oncore within 2 working days of notification to the study coordinator.

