9.0 Safety and Effectiveness Assessments

The primary goal of this pilot study is to determine if MRI with multiparametric sequences mpMRI can be used as a mapping tool for correlation with histopathology results, providing a more informed method for the delivery of focal hypofractionation treatments. Hypofractionated radiation using SBRT is a promising tool for delivery with intent to cure. The use of focal partial prostate SBRT should show lower toxicity, and will be evaluated for equivalent efficacy. A co-primary end point of the pilot study will be to show that patients maintain acceptable HRQOL status as compared to baseline. There will be two co-primary endpoints based on summary scores from the bowel and urinary domains of the EPIC questionnaire. Although HRQOL is collected at multiple time points, it has been decided that EPIC, EQ D5 and Sexual Medication/Device Screening data collected at 6, 12 and 24 months post therapy will be compared to baseline to test the primary hypothesis. The percentage of patients with change in EPIC bowel domain score (baseline to 1-year) that was worse than 5 points and a change in EPIC urinary domain score that was worse than 2 points are felt to be clinically meaningful endpoints to assess for tolerability and safety. A rate for the worse-than-5 point change in bowel score of up to 35% of patients will be considered acceptable, with a rate $\geq 55\%$ specified as unacceptable. Similarly, a rate for the worse-than-2 point change in urinary score of up to 40% will be considered acceptable, with a rate $\geq 60\%$ unacceptable. The PSA results along with serial MRI assessments will be used to test the hypothesis of equivalent disease control compared to historical data for whole gland therapy using SBRT. Standard of care quality of life assessments International Prostate Symptom Score (IPSS) and sexual health inventory for men (SHIM) scores will be acquired as part of the standard care prior to and following SBRT. When collected, this data will be collected and reported.

Analysis of the Primary Endpoints

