9.1 Safety and Efficacy Endpoints

Assessment of early clinical outcomes in focal SBRT for low risk prostate cancer patients. Twenty-four hormone naïve low to intermediate risk prostate cancer patients will be screened for PSA level, acute toxicities and quality of life (QOL) measures at baseline and twelve will be followed at longitudinal follow-up appointments.

Acute and Late GI and GU Adverse Events (AEs)

Adverse events are evaluated by the CTEP Active Version of the NCI Common Terminology Criteria for Adverse Events (CTCAE). We will record in Oncore the highest grade reported during a reporting period. The treatment-related attribution includes definitely, probably or possibly related to treatment. An acute adverse event is defined as the first occurrence of worst severity of the adverse event ≤ 30 days after the completion of RT. We will evaluate the acute radiation therapy-related adverse events. Specifically, we are interested in the percentage of acute GI and GU Grade 3+ adverse events that may occur, which is considered to be similar to the high RT dose arm of RTOG 0126 in terms of RT dose. If our partial prostate hypofractionated regimen has an acceptable percentage, then it will be deemed to have an acceptable adverse event profile. We will report the percentage for the regimen as well as the one-sided 97.5% confidence interval. For example, the number of patients in the high dose arm of RTOG 0126 Phase II reported that 1% of patients experienced Grade 3+ GI/GU acute toxicity, with no patient experiencing Grade 4 or 5 toxicities (citation) should be greater than this pilot study. A late adverse event is defined as the first occurrence of worst severity of adverse event > 180 days after RT completion. Late Grade 3+ GU/GI toxicity information will be collected and reported also.

PSA Failure

Failure occurs when the PSA is first noted to be 2 ng/mL or more than the patient's nadir value post RT completion (Phoenix, Abramowitz 2009). PSA failure at 6, 12 and 24 months following RT will be estimated for the series by the cumulative incidence method (Gray 1988). Also, confidence intervals will be reported.

Disease-Free Survival (DFS)

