10.2 Statistics

Statistical Considerations

Chi-square and cluster re-sampling analyses will be used to correlate suspicion on multiparametric magnetic resonance imaging and the incidence of cancer detected on biopsy.

The primary goal of this study is to evaluate acute and late toxicities. In addition clinical data will be collected to monitor for tumor control. Digital rectal examination (DRE) and serum prostate antigen (PSA) will be evaluated every 3 months for two years. Toxicity will be evaluated EPIC EQ D5, Sexual Medication, Device Screening Questionnaires completed by the patients or in conversation with the patient by the clinical staff, at baseline, 6, 12 and 24 months following the end of radiation therapy (+/- 14 days). Rates of acute and late side effects and adverse events will be summarized as proportions, with 95% confidence intervals.

Biochemical failure will be based on PSA values using the Phoenix definition (clinical nadir +2ng/mL). Data from all patients will be pooled. Survival rates estimated from the Kaplan-Meier curves will be estimated with 95% confidence intervals. We will also track virtual treatment plans based on standard models for treatment to the whole gland versus partial gland MRI-TPUS validated planning to report change in dosimetric parameters of the focal SBRT versus traditional whole-gland treatment plans for statistical comparison.

Either a positive DRE or rising PSA may be used as clinical indication for additional MRI surveillance. When additional MRI are available, tumor volume will be summarized by mean \pm STD and the difference between two time points (pre and post treatment) will be examined using paired T-test. Radiographic efficacy will be summarized by calculating Kaplan-Meier curves for the following: disease-free survival, time to local progression, time to distant failure. Descriptive reports of RECIST (1.1) and volumetric findings will be provided.

Acute/Late Toxicity and Quality of Life Measurements

Using multivariate analysis, we will report acute and late (>180 days post SBRT) rates of GI toxicity with dose-volume histogram. We will also report time to event analyses collected for all available HRQOL data collected.

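### The SAE definition closes 30 days after treatment, so read literally a serious late radiation injury misses the SAE process, although late toxicity is a stated primary goal and follow-up runs to 24 months

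*Combined protocol and SAP*

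**What the plan says.** Section 6.2 (Radiation Therapy Adverse Events) defines an SAE as "Any adverse experience occurring during any part of protocol treatment and 30 days after that results in any of the following outcomes". The outcomes listed are death, a life-threatening experience, hospitalisation or its prolongation, persistent or significant disability, and birth defect. A further paragraph says that important medical events falling short of death, threat to life or hospitalisation "may be considered an SAE, when, based upon medical judgment, they may jeopardize the patient"; it repeats no time limit.

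The same section sets the handling: "The SAE is to be entered into Oncore and the regulatory coordinator and DSTC coordinators will then work with the PI". The purpose of that step is submission to both the IRB and the DSTC. OnCore entry is due within 2 working days of the study coordinator being notified.

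Section 9.1 defines an acute event as the "first occurrence of worst severity of the adverse event ≤ 30 days after the completion of RT". It then says: "A late adverse event is defined as the first occurrence of worst severity of adverse event > 180 days after RT completion". It adds: "Late Grade 3+ GU/GI toxicity information will be collected and reported also".

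Section 10.2 states: "The primary goal of this study is to evaluate acute and late toxicities". Section 9.0 gives a different primary goal: "The primary goal of this pilot study is to determine if MRI with multiparametric sequences mpMRI can be used as a mapping tool", with bowel and urinary EPIC scores as co-primary endpoints. Sections 7.2 and 7.3 schedule follow-up with adverse event assessment to 24 months.

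**The concern.** For radiotherapy to the prostate, the injuries of most interest to a late-toxicity objective are rectal and bladder events that appear months after treatment. A definition that ends at 30 days is built around the acute phase. If a man is admitted at 9 months with a treatment-related rectal injury, the protocol's own definition says that this is not an SAE, and the handling written for SAEs does not start.

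Timing matters because the study enrols slowly and section 6.1.1 calls the three-fraction regimen novel. Serious late injury in the first men could occur while later men are still to be treated. The plan ties no pausing step to a count of toxicities, so prompt passage of serious events to the DSTC is one of its main safeguards.

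**Working it through.** The plan gives no figure to reproduce. The check compares windows, taking 24 months as 730 days from the end of radiotherapy.

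**Windows after the end of radiotherapy**
- SAE definition (6.2): days 0 to 30.
- Acute event (9.1): days 0 to 30.
- Evaluable for acute toxicity (9.2): to day 90.
- Late event (9.1): after day 180, so 730 − 180 = 550 days of follow-up.
- Neither acute nor late under 9.1: days 31 to 180, which is 180 − 30 = 150 days. Days 31 to 90 of this stretch still count towards acute evaluability in 9.2.
- Overlap of the SAE window with the late period: 0 days.

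**Visits (7.3), at 30.4375 days per month:** day 30, then about days 91, 183, 274, 365, 457, 548, 639 and 730. That is nine visits, eight after day 30 and seven after day 180. The 6-month visit clears day 180 by only about 3 days. Adverse events are assessed at all nine.

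**Does the medical-judgment paragraph close the gap?** Not for the events that matter most. Its conjunctions are loose, but its evident subject is events that do not result in death, threaten life or require hospitalisation. Even if it is free of the 30-day limit, the outcome is uneven: a lesser late event could become an SAE by judgment, while a late death or admission would not qualify under the main definition.

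**What happens to a serious late event by each route?**
- SAE entry within 2 working days and SAE submission to the IRB and DSTC (6.2): written for SAEs, so not triggered on a literal reading.
- Reporting table (6.2): sorted by grade, attribution and expectedness, with no day limit. Related deaths are due in 5 working days and related unexpected Grade 3 or 4 events in 10. Related expected Grade 3 or 4 events are summarised at continuing review. The table follows directly on a sentence about SAEs, so whether it governs late events that are not SAEs is a matter of reading.
- Grade 3 and above to OnCore, reported under the data and safety monitoring plan (9.2): no day limit, and no deadline stated there.
- Unanticipated events to the IRB, with a provision to pause (9.2): applies throughout the study. Proctitis, hematochezia and hematuria are listed in 6.2 as potential side effects, so a late rectal or bladder injury may be judged anticipated and not take this route.

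**Could the notice matter during accrual?** Twelve men are planned over 24 months, at most 6 per year. Assume steady accrual at that ceiling and that the first man finishes treatment about 2 months after opening. He passes day 180 at about month 8. That leaves 24 − 8 = 16 months, or 16 × 6/12 = 8 men still to enrol.

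**The case against.** The strongest reply is that late toxicity is well covered without the SAE label. It is assessed at every follow-up visit, late Grade 3+ GI/GU events are collected and reported, Grade 3+ events enter OnCore under the monitoring plan, and unanticipated events go to the IRB at any time. This stands, and it limits the point to SAE status and prompt DSTC notice. A reader might infer that late injury goes undetected or unanalysed; the documents do not support that.

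A reader might also infer that no late radiation injury could be reported as an SAE under any circumstances. That is too absolute. The medical-judgment paragraph carries no time limit of its own, although it can be read as inheriting the 30 days. Section 6.2 also defers to a cancer center SAE policy, and section 9.2 to a monitoring plan, neither of which is reproduced; either may cover late related events.

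The gain in IRB timing is modest. Even inside 30 days, the table sends a related, expected Grade 3 or 4 event only to continuing review. For such events the amendment mainly adds the 2-working-day entry and the DSTC submission.

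It is tempting to divide 30 by 730 and say that the definition captures about 4% of serious events. That ratio is a share of calendar days. The documents contain no data on event timing, and events outside the window still reach other routes.

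Finally, late toxicity is the primary goal only in section 10.2, since section 9.0 states another. The mismatch remains on either reading, because section 9.1 makes late toxicity a reported endpoint.

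**Conclusion.** The point holds in limited form. The dated SAE definition does not match the late-toxicity goal or the 24-month follow-up. On a literal reading, a late treatment-related death, life-threatening event, hospitalisation or disability is outside the definition, and so outside the 2-working-day OnCore entry and the SAE submission to the DSTC. The overlap between the two windows is nil, and seven of the nine post-treatment visits fall in the late period.

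The conclusion assumes that section 6.2 is applied as written and that the unreproduced center policy does not widen it. The accrual illustration further assumes steady enrolment at the stated ceiling. No estimate of the number of events affected can be made from the documents. The defect concerns safety oversight and biases no analysis, but it is worth amending because the correction is small and could inform the treatment of later men.

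**What to change.** In section 6.2, keep the existing window and add after the 30-day limit: *or at any later time during follow-up if possibly, probably or definitely related to study treatment*. These attribution terms are already used in the section 6.2 reporting table.

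In the same amendment:
- State in section 6.2 whether the reporting table applies to all adverse events or only to SAEs, and confirm that the cited center policy agrees with the extended definition.
- Reconcile the 30-day acute window in 9.1 with the 90-day evaluability window in 9.2, and say how events on days 31 to 180 are classified.
- Align the reporting routes in 9.2 and the primary goals in 9.0 and 10.2 with the result.

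The cost is one clause plus editorial reconciliation, and slightly more SAE reporting across 12 treated men. Treatment, visits and sample size are unchanged.

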7.0 Study Procedures

Screening procedures will be performed up to 28 days before registration unless otherwise stated. Study visits will have a 2-3 study window unless otherwise stated.

7.1 Screening Visits

Screening Visit – visit #1

- Informed Consent (for patients who meet screening criteria)
- Demographics
- Medical History
- Height
- Weight
- Vitals including blood pressure, pulse, respiratory rate, temperature
- Physical examination
- Concomitant medication assessment
- ECOG performance status
- Assessment of baseline symptoms
- Quality of Life scores (standard of care) IPSS and SHIM
- Research Quality of Life scores (EPIC, EPIC Supplement Sexual Medicines/Devices, EQ-5D)
- Laboratory Studies:
 - Complete Blood Count (CBC) with differential, platelets

- Serum Chemistries: albumin, alkaline phosphatase, total bilirubin, bicarbonate, BUN, calcium, chloride, creatinine, glucose, potassium, total protein, SGOT [AST], SGPT [ALT], sodium.
- Calculated creatinine clearance will be done if creatinine and/or BUN are abnormal
- Testosterone
- Pelvic mpMRI with contrast and multiparametric sequences (SOC for staging) (must be within 180 days of screening visit)
- Bone Scan when clinically indicated per standard-of-care (must be within 90 days of screening visit)
- PSA (must be within 90 days of screening visit)
- DRE (must be within 90 days of screening visit)

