4.0 Subject Selection and Withdrawal

4.1 General Characteristics of the Proposed Subject Population

Histologically confirmed diagnosis of adenocarcinoma of the prostate. Gleason scores $\leq 7(3+4)$; Clinical stage T1-2a; PSA ≤ 10 ng/mL (PSA should not be obtained within 10 days after prostate biopsy).

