4.3 Inclusion Criteria

Patients with positive diagnostic prostate biopsy with or without positive digital rectal exam (DRE) (clinical stage \leq T1-T2a or T1cN0M0), Gleason score $\leq 7(3+4)$, with a PSA ≤ 10 ng/mL and routine staging work-up consistent with a diagnosis of localized prostate cancer. Patients eligible for either whole-gland therapy or active surveillance will use the staging MRI to screen for intraprostatic disease burden. Patients having a single focal dominate lesions greater than 5 mm in size confirmed with imaging and biopsy will be eligible for this trial. Patients (≤ 6 total per year) will be treated with focal SBRT delivering on study to 29.25 Gy in 3 fractions (9.75 Gy per fraction) to involved sub-volume. Eligible patients must be able to undergo an MRI with contrast.

Patient's Name _____

Medical Record # _____

Research Nurse /
Study Coordinator Signature: _____ Date _____

Treating Physician [Print] _____

Treating Physician Signature: _____ Date _____

Patients must meet all of the following inclusion criteria to be eligible for enrollment:

- ____ 4.3.1 Patients must have a histologically confirmed diagnosis of adenocarcinoma of the prostate.
- ____ 4.3.2 Patient must have a history/physical examination with digital rectal examination of the prostate within 90 days prior to screening
- ____ 4.3.3 Age ≥ 18 years. Because no dosing or adverse event data are currently available on the use of the study treatment in patients <18 years of age, children are excluded from this study.
- ____ 4.3.4 ECOG Performance status must be level 0 or 1 within 60 days prior to registration [See Appendix A].

ECOG PS = _____
Date: _____

- ____ 4.3.5 Patient must have a histological evaluation of the prostate biopsy with assignment of a Gleason score to the biopsy material; Gleason scores $\leq 7(3+4)$
- ____ 4.3.6 Patients must have adequate renal function as defined below:

Serum Creatinine $<$ or $=$ 1.5 times the ULN (Normal: ≤ 1.17 mL/min/1.73 m²)
Serum Creatinine: _____
Date of Test: _____

- ____ 4.3.7 Clinical stage a $</=$ T1-T2a (AJCC 7th edition)
- ____ 4.3.8 PSA ≤ 10 ng/mL within 90 days prior to registration. PSA should not be obtained within 10 days after prostate biopsy.
- ____ 4.3.9 Subjects must have the ability to understand and the willingness to sign a written informed consent document.
- ____ 4.3.10 Patient willing and able to complete the Expanded Prostate Cancer Index

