7.2 Study Visits

Biopsy and Fiducial Placement – visit #2

- Weight
- Vitals including blood pressure, pulse, respiratory rate, temperature
- Physical examination
- Guided biopsy
- Fiducial placement

MRI and CT scans for RT SIM – visit #3

- RT CT (with contrast unless contraindicated) for simulation
- Pelvic MRI with Contrast
- Pelvic CT for SIM

SBRT #1 – visit #4

- RT treatment

SBRT #2 – visit #5

- RT treatment

MRI – visit #6

- Pelvic mpMRI with Contrast

SBRT #3 – visit #7

- Adverse events assessment (may be completed by telephone call within 7 days post visit 7)
- RT treatment

Follow up, every 3 months for up to 24 months – visits #8 - #16

- Weight
- Vitals including blood pressure, pulse, respiratory rate, temperature
- Physical examination
- ECOG performance status
- Quality of life Score standard of care IPSS and SHIM Scores
- Adverse events assessment

Post SBRT Follow up Measurements

- PSA to be completed at ALL follow up visits

- DRE to be completed at **ALL** follow up visits
- Serum Creatinine and BUN Blood Draw at **6, 12, and 24** months follow up prior to MRI
- Pelvic MRI to be completed at **6, 12, and 24** month follow up visits with contrast
- EPIC EQ D5, Sexual Medication/Device screening to be completed at **6, 12 and 24** months

Any positive results for staging Post RT (positive digital rectal exam or evidence of biochemical failure using the clinical nadir +2 definition (serum PSA rise above 2ng/mL from the post therapy nadir (Phoenix, Abramowitz 2007) may trigger clinical indication for SOC staging MRI to rule out disease progression. If acquired, this data will be collected for comparison to other serial MRI data. Should a patient be deemed to have failed therapy using the Phoenix criteria (nadir +2ng/mL PSA) the subject/s will be referred for consultation for review of options for salvage therapy, and if the patient elects a second treatment the subject will be taken off study.

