
1  TIME POINT⁽¹⁾
 
1 Pretreatment 2 One year follow-up 3 Two year follow-up 4 Five year follow-up
 
2  WAS PATIENT QUESTIONNAIRE COMPLETED?⁽²⁾
 
1 No (Skip to question 3) 2 Yes
 
2A DATE PATIENT QUESTIONNAIRE COMPLETED ____ - ____ - ____⁽³⁾
 
3  REASON PATIENT QUESTIONNAIRE WAS NOT COMPLETED⁽⁴⁾
 
0 Not applicable, questionnaire was completed 1 Patient refused due to illness 2 Patient refused for other reason, specify _____⁽⁵⁾ 3 Unable to contact patient 4 Institutional error 5 Tool not available in patient's language 6 Other reason, specify _____⁽⁶⁾ 9 Unknown
	
4  SPECIFY METHOD OF COMPLETION⁽⁷⁾
 
1 At appointment 2 By mail 3 By telephone 9 Unknown
 
5  DID THE PATIENT REQUIRE ANY ASSISTANCE IN COMPLETING THE QUESTIONNAIRE?⁽⁸⁾
 
1 No 2 Yes 9 Unknown if assistance was given
 
6  SPECIFY THE PERSON WHO ASSISTED THE PATIENT⁽⁹⁾
 
1 Staff member 2 Family 3 Other, specify _____⁽¹⁰⁾ 9 Unknown
 
7  EXTENT OF THE ASSISTANCE⁽¹¹⁾
 
1 Read items to patient 2 Interpreted items for patient 3 Marked items per patient's response 4 Combination of above, specify _____⁽¹²⁾ 5 Other, specify _____⁽¹³⁾ 9 Unknown

--	--

Signature of person completing this form⁽¹⁴⁾Date form completed⁽¹⁵⁾

The Expanded Prostate Cancer Index Composite (EPIC)

This questionnaire is designed to measure Quality of Life issues in patients with Prostate Cancer. To help us get the most accurate measurement, it is important that you answer all questions honestly and completely.

Remember, as with all medical records, information contained within this survey will remain strictly confidential.

Today's Date: ____ / ____ / ____

Name: (Last, First, M.I.) _____

Date of Birth: ____ / ____ / ____

URINARY FUNCTION

This section is about your urinary habits. Please consider **ONLY THE LAST 4 WEEKS**.

1. Over the **past 4 weeks**, how often have you leaked urine?

More than once a day.....	1
About once a day.....	2
More than once a week	3
About once a week	4
Rarely or never	5

(Circle one number)

2. Over the **past 4 weeks**, how often have you urinated blood?

More than once a day.....	1
About once a day.....	2
More than once a week	3
About once a week	4
Rarely or never	5

(Circle one number)

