3. Over the **past 4 weeks**, how often have you had pain or burning with urination?

More than once a day.....	1
About once a day.....	2
More than once a week	3
About once a week	4
Rarely or never	5

(Circle one number)

4. Which of the following best describes your urinary control **during the last 4 weeks**?

No urinary control whatsoever.....	1
Frequent dribbling.....	2
Occasional dribbling	3
Total control	4

(Circle one number)

5. How many pads or adult diapers per day did you usually use to control leakage **during the last 4 weeks**?

None.....	0
1 pad per day.....	1
2 pads per day	2
3 or more pads per day.....	3

(Circle one number)

6. How big a problem, if any, has each of the following been for you **during the last 4 weeks?**

(Circle one number on each line)	No problem	Very Small Problem	Small Problem	Moderate Problem	Big Problem
a. Dripping or leaking urine	0	1	2	3	4
b. Pain or burning on urination	0	1	2	3	4
c. Bleeding with urination	0	1	2	3	4
d. Weak urine stream or incomplete emptying	0	1	2	3	4
e. Waking up to urinate	0	1	2	3	4
f. Need to urinate frequently during the day	0	1	2	3	4

7. Overall, how big a problem has your urinary function been for you **during the last 4 weeks?**

No problem	1	
Very small problem	2	
Small problem.....	3	(Circle one number)
Moderate problem.....	4	
Big problem.....	5	

BOWEL HABITS

The next section is about your bowel habits and abdominal pain.
Please consider **ONLY THE LAST 4 WEEKS.**

8. How often have you had rectal urgency (felt like I had to pass stool, but did not) **during the last 4 weeks?**

More than once a day.....	1	
About once a day.....	2	
More than once a week	3	
About once a week	4	
Rarely or never	5	

9. How often have you had uncontrolled leakage of stool or feces?

More than once a day.....	1	
About once a day.....	2	
More than once a week	3	
About once a week	4	
Rarely or never	5	

10. How often have you had stools (bowel movements) that were loose or liquid (no form, watery, mushy) **during the last 4 weeks?**

Never.....	1	
Rarely.....	2	
About half the time.....	3	
Usually.....	4	
Always.....	5	

11. How often have you had bloody stools **during the last 4 weeks?**

Never.....1
Rarely.....2
About half the time.....3
Usually.....4
Always.....5

(Circle one number)

12. How often have your bowel movements been painful **during the last 4 weeks?**

Never.....1
Rarely.....2
About half the time.....3
Usually.....4
Always.....5

(Circle one number)

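### Baseline EPIC is taken once, at screening, with a 4-week recall and no minimum interval after the last prostate biopsy, so biopsy symptoms can lower the baseline and hide 1-year worsening in both EPIC co-primaries

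*Combined protocol and SAP*

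**What the plan says.** - **When baseline is taken.** Section 7.1 lists "Research Quality of Life scores (EPIC, EPIC Supplement Sexual Medicines/Devices, EQ-5D") under screening visit 1. Section 7.0 gives the only general window: "Screening procedures will be performed up to 28 days before registration unless otherwise stated". It is tied to registration, not to a biopsy. In the calendar (7.3) the next EPIC is at 6 months after radiotherapy.
- **What comes before it.** Section 4.3 admits "Patients with positive diagnostic prostate biopsy with or without positive digital rectal exam (DRE"), with no date limit on that biopsy. Section 6.1 also provides for men who have already had an MRI-targeted biopsy.
- **What comes after it.** "Biopsy and Fiducial Placement – visit #2" (7.2) follows screening, so the study's own guided biopsy does not touch the visit 1 form.
- **What EPIC asks.** The urinary and bowel sections in Appendix 3 are limited to the last 4 weeks. They ask "how often have you urinated blood" and "How often have you had bloody stools during the last 4 weeks", and also cover burning on urination, painful bowel movements and rectal pain. Urinary and rectal bleeding and urinary pain each appear in both a frequency item and a bother item.
- **What is protected.** Sections 4.1 and 4.3.8 say "PSA should not be obtained within 10 days after prostate biopsy". No such rule exists for EPIC.
- **How baseline is used.** The bowel co-primary in section 9.0 is "The percentage of patients with change in EPIC bowel domain score (baseline to 1-year) that was worse than 5 points"; the urinary co-primary uses a decline of more than 2 points. Bowel rates up to 35% are acceptable and 55% or more unacceptable; for urinary the limits are 40% and 60%.

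**The concern.** Section 12.1 names bleeding and infection as biopsy risks and likens them to those of the diagnostic biopsy. If the 4-week recall at visit 1 covers the days after a biopsy, the form measures a temporarily worsened state rather than the man's usual pre-treatment state. Symptoms that have cleared by 1 year can only push the recorded baseline down. The 1-year decline then looks smaller, and a man whose function really fell past the threshold may not be counted. The error runs one way, toward declaring toxicity acceptable. With no second pre-treatment EPIC, a low baseline score cannot be re-measured once treatment has started. The PSA rule shows that the plan already treats a recent biopsy as able to distort a baseline measurement.

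**Working it through.** The plan states no figure for this point, so there is nothing to reproduce. The check asks how large a biopsy effect would be against the thresholds, and how far it would move the event rates.

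**1. Points per item level.** Assumption: each item is scaled 0-100 and the domain score is the item mean. The documents print the items but no scoring algorithm.
- Urinary items: 1-5 (5) + 6a-f (6) + 7 (1) = 12. One level on a 5-level item = 25/12 = 2.08 points; on two items, 2 × 25/12 = 4.17.
- Bowel items: 8-14 (7) + 15a-f (6) + 16 (1) = 14. One level = 25/14 = 1.79 points; on two items, 3.57; on three, 5.36.

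One urinary level therefore already exceeds the 2-point threshold. Two bowel levels use up 3.57 of the 5 points.

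**2. An attainable bowel record under this scoring.**
- Usual score, four levels below the maximum: 100 − 4 × 1.786 = 92.86.
- Biopsy bleeding adds one level on item 11 and one on 15e, so recorded baseline = 100 − 6 × 1.786 = 89.29.
- Score at 1 year: 100 − 8 × 1.786 = 85.71.
- True change 85.71 − 92.86 = −7.14 (event). Recorded change 85.71 − 89.29 = −3.57 (no event).

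**3. Who can flip.** A baseline shift *s* hides an event only if the true decline lies between the threshold and the threshold plus *s*. For bowel that is between 5 and 8.57 points. A man who falls 15 points is still counted.

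**4. Effect on event rates.** Assumptions: normal change scores, SD of change 10, true rate *p* equal to the protocol's unacceptable limit, and *k* of 12 men with baseline lowered by *s*.

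Observed rate = p − (k/12) × [p − Φ(z_p − s/SD)]

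- Bowel: p = 0.55, z = 0.126, s = 3.57. Φ(0.126 − 0.357) = 0.408; difference 0.142.
- Urinary: p = 0.60, z = 0.253, s = 4.17. Φ(0.253 − 0.417) = 0.435; difference 0.165.

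| Men affected | Bowel: fall in rate (percentage points) | Urinary: fall in rate (percentage points) |
|---|---|---|
| 2 of 12 | 2.4 | 2.7 |
| 4 of 12 | 4.7 | 5.5 |
| 6 of 12 | 7.1 | 8.2 |

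Changing the assumed SD to 12 or 8 gives 2.0 to 8.8 points for bowel and 2.3 to 10.3 for urinary over the same 2 to 6 men.

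**5. Effect on the conclusion.** The plan gives no decision count. Four of 12 (33%) is the largest count inside both acceptable limits, since 5/12 = 42% exceeds 35% and 40%. The exact binomial chance of 4 or fewer at the unacceptable rates is 11.2% for bowel and 5.7% for urinary with no bias. With 6 of 12 men shifted as above, the observed rates are 47.9% and 51.8%, and the chances become about 24% and 16%. With none affected, nothing changes.

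**The case against.** The documents do not say that any man is recently biopsied at visit 1. Men arrive through urology or radiation oncology consultation (4.5), section 7.1 accepts a staging MRI up to 180 days old, and some candidates may come from active surveillance. The interval could be months for all twelve. Section 12.1 gives no frequency or duration for biopsy symptoms, so the item shifts above are assumptions. All of this stands: the bias is possible, not shown.

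A reader might infer that each affected man who would otherwise be an event is lost, so that 2, 4 or 6 men remove 17, 33 or 50 percentage points, against a 20-point gap between the limits. The documents do not support that. Step 3 shows that only men close to the threshold flip, and step 4 gives about 2 to 8 points, which is roughly 0.3 to 1 man of 12.

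A reader might also infer that every quality-of-life comparison is compromised. EQ-5D asks about health today, so the 4-week-recall argument does not reach it, and the items identified here are urinary and bowel only.

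Finally, section 10.2 calls this a proof-of-principle study without adequate power for quality of life. At 4 of 12 the exact 95% interval runs from about 10% to 65%, far wider than the modelled bias. That limits the importance of the point, but sampling error can go either way and this error cannot. Biopsy dates could be recovered from pathology records later; a clean baseline score could not.

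**Conclusion.** The gap is real: one pre-treatment EPIC, a 4-week recall, no minimum interval after biopsy, and both EPIC co-primaries measured from it. Any contamination would hide worsening, and the urinary endpoint is the more exposed because its threshold is about one item level. The size is uncertain. It is zero if no man is recently biopsied, and about 2 to 8 percentage points on the event rate if 2 to 6 of 12 are, given 0-100 item scoring, shifts of 3.6 or 4.2 points, an SD of change of 10 and true rates at the unacceptable limits. This is a moderate design weakness that is cheap to close, not evidence that the co-primaries will be wrong.

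**What to change.** In 7.1 and the study calendar:

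1. Record the date of the most recent prostate biopsy, diagnostic or targeted.
2. If the 4-week recall at visit 1 reaches back to that biopsy or the symptomatic days after it, repeat EPIC on arrival at visit 2, before the guided biopsy and fiducial procedure, and use that form as baseline. A workable trigger is a biopsy less than about 6 weeks earlier: 4 weeks of recall plus an assumed 2 weeks of symptoms. A bare 28-day rule would not do, because a form completed on day 28 still recalls the days just after the biopsy.
3. Do not move visit 2 for this purpose, and do not take baseline after it. The calendar puts simulation 2-3 weeks after fiducials and SBRT 2-3 weeks after that, so a later form could pick up the guided biopsy instead.
4. Report both EPIC co-primaries with and without men whose baseline recall still overlaps the post-biopsy period.

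EQ-5D can stay at visit 1. The cost is one recorded date, one extra questionnaire for some men and one sensitivity analysis. There is no added visit.
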